9.3 Follow-up assessments

9.3.1 Visit 2 (Week 4+1 week)

- Recording of AEs and concomitant medications
- Physical Examination & Medical Review**
- Vital signs inc. pulse, blood pressure, temperature
- Safety bloods (see section 11.1 for list of laboratory tests)
- Bloods for Immunology and biomarkers
- Drug compliance (pill count and drug diary review)
- Uptitration of drug at 80mg dose.
- MRI appointment for next visit booked/date confirmed with patient

- Retinal imaging appointment for next visit booked/date confirmed with patient
- Patient reminded to bring diary card, trial medication bottles with unused trial medication back for the next visit.

** Medical review will encompass any medical or MS-related symptoms that have arisen.

If a patient is unable to attend the clinic at week 4 or within the visit window, a TC will be arranged to check for AEs and acceptability to uptitrate and an appointment nearest to the timeframe will be scheduled.

9.3.2 End of Study treatment visit (Week 16 +1 week)

At this visit, any remaining study medication will be returned to site pharmacy.

- Recording of AEs and concomitant medications
- Physical Examination & Medical Review**
- Vital signs inc. pulse, blood pressure, temperature
- EDSS disability assessment
- MSFC inc. 25FTW, 9HPT
- SDMT
- Questionnaires (MSIS-29v2, MSWsv2, EQ5D5L)
- Safety Bloods (see section 11.1 for list of laboratory tests)
- Bloods for Immunology and biomarkers
- Urine pregnancy test for females of child bearing potential
- MRI inc. ASL questionnaire follow-up
- Retinal Imaging Vascular Function Questionnaire
- Retinal Imaging (Advanced retinal imaging, OCT)
- Drug compliance (pill count and drug diary review)
- MRI appointment booked/date confirmed with patient
- Retinal imaging booked/date confirmed with patient

As at screening/baseline (visit 1), the assessment will take place across two sites. All assessments will take place over two days, one for each site with the option to complete all assessments on one day if feasible.

** Medical review will encompass any medical or MS-related symptoms that have arisen.

If a patient is unable to attend the clinic within the visit window, a TC will be arranged to check for AEs and an appointment nearest to the timeframe will be scheduled.

9.3.3 End of Study Follow-up (Week 20+2 weeks)

The following assessments will be covered:

- Recording of AEs and concomitant medications
- Physical Examination & Medical Review**
- Vital signs inc. pulse, blood pressure, temperature
- EDSS disability assessment
- MSFC inc. 25FTW, 9HPT
- SDMT
- FAB
- Questionnaires (MSIS-29v2, MSWsv2, EQ5D5L)
- Safety Bloods(see section 11.1 for list of laboratory tests)
- Bloods for Immunology and biomarkers
- Urine pregnancy test for females of child bearing potential
- MRI inc. ASL questionnaire follow-up
- Retinal Imaging Vascular Function Questionnaire
- Retinal Imaging(Advanced retinal imaging, OCT)

As at screening/ baseline (visit 1) and end of study treatment visit, the assessment will take place across two sites. All assessments will take place over two days, one for each site with the option to complete all assessments on one day if feasible.

** Medical review will encompass any medical or MS-related symptoms that have arisen.

9.3.4 Unscheduled visits (Between V1-EOS Follow-up)

Participants will be instructed to contact the local study team between scheduled visits should they suspect a relapse or any adverse events that are deemed serious or require further examination. An unscheduled visit (either for or not for a relapse) can occur at the local study team's discretion and the following will be assessed and recorded:

- Recording of AEs and concomitant medications
- Physical Examination & Medical Review**
- Vital signs inc. pulse, blood pressure, temperature
- EDSS disability assessment
- Safety Bloods(see section 11.1 for list of laboratory tests)

** Medical review will encompass any medical or MS-related symptoms that have arisen.

9.3.5 Telephone Follow-up (As required)

Participants may be contacted by a member of the trial team if there are safety concerns or updates to the trial. As stated in appendix 1, the participant as standard will be asked if they have any side effects (as listed in section 4), concomitant medications and adverse events will also be checked. Medical review and drug compliance will be dependent on the circumstances of the participant and the timepoint in the study.

9.3.6 Procedure for emergency telephone contact

An emergency phone will be kept by a medically qualified member of the study team on rotation. They will then advise the patient as per seriousness of the medical emergency as to how they should proceed e.g. A&E admission.

10. Randomisation Procedures

Randomisation will take place at Visit 1. Participants are considered to be enrolled into the trial following consent and the completion of all entry-criteria assessments (carried out on day 1 of visit 1). It may not be possible to complete all visit 1 assessments in one day so visit 1 may occur over 2 days. Randomisation will take place on day 1 of visit 1. The entry-criteria assessments at visit 1 will be prioritised for the purpose of randomisation on day 1 of visit 1, with the advanced retinal imaging and visual assessments (not required to confirm eligibility for the study) carried out on day 2 of visit 1 after randomisation (when visit is across 2 days). The patient will be instructed not to take the study medication until all study assessments are completed on day 2 of visit 1. If visit 1 is completed over 1 day, the patient can take study medication on the evening when all visit assessments are complete.

Screening/baseline visit and eligibility criteria form and randomisation will be performed via an on line system hosted by a specialist company (www.sealedenvelope.com) who will hold the randomisation list (to conceal actual treatment allocation to the research team) and provide 24/7 randomisation services. Detailed instruction on logging in and randomising participants on this system is in the randomisation SOP. After randomisation, the site research team will be given a unique trial randomisation number via email from sealedenvelope.com. Randomisation details of patients will be entered on a trial subject enrolment log and the participant will be given a study specific patient card which will have study title, IMP details, patient ID and contact details of the out of hours contact in cases of emergency. Section 21.3 describes how assignment to treatment groups will be done and the statistical methods used to generate randomisation.

10.1 Treatment Schedule

The starting dose at baseline will be 40mg of Simvastatin or placebo (one tablet) to be taken orally in the evening. This will be up-titrated at Visit 2 (week 4) to 80mg (two tablets) if all safety parameters have been met at visit 2.

Participants will be allocated one bottle each containing 220 tablets for the duration of the study. There will therefore be one drug dispensation at baseline and the patient will be reminded to up titrate after one month at Visit 2.

10.2 Dose Modifications

If the participant is able to tolerate the 40 mg dose, after 4 weeks they will be uptitrated to 80 mg. If the participant is unable to tolerate the 40 mg dose at 4 weeks or at any point during the study, the medication will be withdrawn (e.g. any significant side effect as listed in section 4). If the participant is able to tolerate the 40 mg but not the 80 mg dose, then the participant will continue on this dose until the end of the study. They will then be re-approached at week 12 to uptitrate to 80mg if tolerated. If this is not tolerated, they will remain on 40 mg until the end of study.

Participants who were unable to tolerate the 40 mg dose at 4 weeks, and were withdrawn at this stage, will be re-approached to re-start the drug at 40 mg at week 12. Those participants who were unable to tolerate 40 mg beyond 4 weeks will have their study medication withdrawn and not re-approached at week 12.

This assessment will be made by the treating physician. The final decision will be made by the CI. The uptitration is to ensure that the end of study MRI is conducted on treatment.

See section 14.2 for treatment stopping rules.

11 Laboratory Assessments and Procedures

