9.2 Visit 1 Screening/Baseline combined assessment (Day 0)

At this visit (which may be conducted over two days), the following will be assessed:

- Informed consent
- Medical History & Contraindications
- Physical examination & Medical review**
- Vital signs inc. pulse, blood pressure, temperature
- Concomitant medications
- EDSS disability assessment
- MSFC inc. 25FTW, 9HPT
- SDMT
- FAB
- Questionnaires (MSIS-29v2, MSWsv2, EQ5D5L)
- Safety Bloods (see section 11.1 for list of laboratory tests)
- Bloods for Immunology and biomarkers
- Urine pregnancy test for females of child bearing potential
- MRI inc. ASL / Questionnaire
- Modified Vascular Function Retinal Imaging Questionnaire
- Visual assessment (likely to take place on day 2 of this visit)
- Retinal Imaging (Advanced retinal imaging, OCT – likely to take place on day 2 of this visit)
- Full eligibility assessment

- Randomisation (see section 10)
- Drug dispensation at 40mg dose (see section 10.1) * .
- Drug diary issued
- Emergency telephone contact given

Participants will be advised on the administration of the medication and will be given a study specific patient card which will have study title, IMP details, patient ID and contact details of the out of hours contact in cases of emergency (see section 9.3.6). A drug diary will also be issued for participants to document compliance to IMP.

Participants will be reminded to bring the drug diary to the next visit.

This visit will take place across two sites. Visit 1 assessments will take place over two days, one for each site with the option to complete all assessments on one day if feasible. Randomisation and drug dispensation will take place on day 1 of visit 1.

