Appendix 1 - schedule of assessments

Visits	Visit 0 Pre- screening	Visit 1* (Combined Screening/ Baseline)	Visit 2	Visit 3* (End of Study Treatment Visit)	Visit 4* (End of Study Follow-up)	Unscheduled (inc. relapse if indicated)	Telephone / e-mail Follow Up
Visit Windows (1 week is equivalent to 7 days e.g. 4 weeks (1 month) is equivalent to 28 days)	within 8 weeks	Day 0	Week 4 (+1 week)	Week 16 (+1 week)	Week 20 (+2 weeks)	Between V1 to EOS Follow-up	As required
Pre-screening questionnaire	X						
Inclusion/Exclusion criteria review	X	X					X
Informed consent		X					
Medical history		X					
Con-meds		X	X	X	X	X	X
Medical review ¹		X	X	X	X	X	X
Recording of AEs			X	X	X	X	X
Physical examination		X	X	X	X	X	
Vital Signs		X	X	X	X	X	
Disability Assessment (EDSS)		X		X	X	X	
MSFC (9HPT, 25TFW)		X		X	X		
SDMT		X		X	X		
FAB		X			X		
MSIS-29v2		X		X	X		
MSWSv2		X		X	X		
EQ5D5L		X		X	X		

Visits	Visit 0 Pre- screening	Visit 1* (Combined Screening/ Baseline)	Visit 2	Visit 3* (End of Study Treatment Visit)	Visit 4* (End of Study Follow-up)	Unscheduled (inc. relapse if indicated)	Telephone / e-mail Follow Up
Visit Windows (1 week is equivalent to 7 days e.g. 4 weeks (1 month) is equivalent to 28 days)	within 8 weeks	Day 0	Week 4 (+1 week)	Week 16 (+1 week)	Week 20 (+2 weeks)	Between V1 to EOS Follow-up	As required
Safety bloods (see section 11.1 for list of laboratory tests)		X	X	X	X	X	
Urine pregnancy test ⁴		X		X	X		
Immunology and biomarkers		X	X	X	X		
MRI		X		X	X		
ASL questionnaire		X					
ASL questionnaire follow-up				X	X		
Visual assessment		X					
Retinal Imaging Vascular Assessment Questionnaire		X		X	X		
Advanced retinal imaging inc. OCT*		X		X	X		
Randomisation		X					
Drug dispensed ³		X (40mg)					
Drug uptitration ³			X (80 mg)				
Drug Diary issued		X					
Confirmation to dose ²		X					
Drug accountability (diary) ⁵			X	X			
Drug compliance ⁵			X	X			X
Telephone contact							X

^{*} This visit will take place across two sites. The assessments may be split across two days. Day 1 assessments will take place at the UCL Institute of Neurology & National hospital for neurology and neurosurgery and day 2 assessments (visual assessment and Advanced Retinal Imaging) will take place at Moorfields Eye Hospital. Patients will be dispensed the drug on Day 1 of visit 1 but will be instructed not to take the drug until the evening of Day 2 of visit 1 (if over 2 days) after all ophthalmic assessments are completed. See Section 10 for full details.

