¹ This will encompass any medical or MS-related symptoms that have arisen between Visit 1 and subsequent visits.

² Study medication must only be dispensed after randomisation once all day 1 of visit 1 assessments have been completed and the relevant safety reports have been obtained. Patients will be dispensed the drug on Day 1 of visit 1 but will be instructed not to take the drug until the evening of Day 2 (if over 2 days) of visit 1 after all ophthalmic assessments are completed. See Section 10 for full details.

³ Participants will be allocated 220 tablets each for the duration of the study. There will therefore be one drug release at baseline and the patient will be reminded to uptitrate after one month at Visit 2. The patient will take 40mg x 2 tablets for the dose of 80mg for a period of 12 weeks. The neurologist will issue the drugs, diary and record compliance at the relevant visits.

For the purpose of safety, the study participant will be contacted by telephone and adverse events assessed by the neurologist. If there are no issues identified, the participant will be advised to take the study medication and encouraged to contact a member of the research team if problems subsequently arise.

⁴ For female subjects only

⁵ This will include a drug diary review and pills count.

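### Section 10.2 allows a week-12 restart of 40 mg after a week-4 withdrawal, with no repeat pregnancy test required and contraception during the pause left unclear

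*Protocol*

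**What the plan says.** **Restart.** Under Protocol 10.2, a participant who cannot tolerate 40 mg at week 4 is withdrawn from the drug and later "will be re-approached to re-start the drug at 40 mg at week 12". The treating physician assesses, and "The final decision will be made by the CI". The section states no other condition. Those held on 40 mg are handled separately: "They will then be re-approached at week 12 to uptitrate to 80mg if tolerated".

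**Pregnancy testing.** Criterion 5 in 8.1.1 requires a negative test in the 7 days before randomisation. Visit 1 on Day 0 (9.2) lists "Urine pregnancy test for females of child bearing potential", and the week-16 and week-20 visits (9.3.2, 9.3.3) list the same item. Appendix 1 marks those three visits only. There is no week-12 visit.

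**Contraception.** Criterion 4 in 8.1.1, repeated in the synopsis (2.1), runs from consent to six weeks after treatment discontinuation. It does not address an interruption. Section 14.2, item 7, gives inability to tolerate 40 mg as a reason for discontinuing treatment.

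**Reason for the test.** The pregnancy row of section 4 says that safety in pregnancy is not established, excludes pregnant women and relies on a test before enrolment.

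**The concern.** Before the first exposure, the protocol asks for a recent negative test. Before the second, it asks for a clinical judgement only, although a woman may by then have been off the drug for about two months.

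The contraception wording adds to this. A participant withdrawn at week 4 could reasonably take her treatment as discontinued and count six weeks from that date. On that reading her duty has ended when she is asked to take the drug again. A site following 10.2 as written could then restart simvastatin in a woman with an unrecognised pregnancy. What is at stake is avoidable fetal exposure to a drug whose safety in pregnancy the protocol calls unestablished.

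**Working it through.** The plan gives no figure to reproduce. The check is calendar arithmetic and a reading of each place where a test could be required.

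**Inputs.** Test and randomisation at Visit 1, Day 0 (9.2). Visit 2 at week 4, window +1 week (9.3.1). Restart at week 12, taken as exact because 10.2 gives no window. End-of-treatment visit at week 16, window +1 week (9.3.2). Contraception to 6 weeks after discontinuation (criterion 4). One week is 7 days.

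**Intervals.**

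- Age of the Day 0 test at restart: 12 × 7 = 84 days.
- Time off drug if dosing stops at Visit 2: (12 − 4) × 7 = 56 days, or (12 − 5) × 7 = 49 days. An earlier stop would lengthen this.
- Restart to next scheduled test: (16 − 12) × 7 = 28 days, or (17 − 12) × 7 = 35 days.
- End of contraception if the week-4 withdrawal counts: 4 + 6 = week 10, or 5 + 6 = week 11. Gap before restart: 12 − 10 = 2 weeks, or 12 − 11 = 1 week.
- Gap if discontinuation means the final stop: 0.

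**Could another provision require the test?**

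- *Visit 2 and unscheduled visits (9.3.1, 9.3.4).* Neither list names a pregnancy test. Both refer to 11.1 for the safety bloods, and 11.1 also lists a urine dipstick. But Appendix 1 leaves the pregnancy-test cell blank in both columns, and the visits that do test list it separately from safety bloods.
- *Telephone contacts.* Appendix 1 marks "Inclusion/Exclusion criteria review" in this column. Criterion 5 is tied to randomisation, so the Day 0 result still satisfies it. Asking about criterion 13 (pregnant or planning pregnancy) would miss an unrecognised pregnancy.
- *Appendix 1, footnote 3.* "For the purpose of safety, the study participant will be contacted by telephone and adverse events assessed by the neurologist". This covers adverse events, not a test.
- *Reporting duties (criterion 4, section 17).* These act only once a pregnancy is known.
- *Dispensing (10.1).* All tablets are issued once, at baseline. No dispensing check is written for a restart.

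**Number affected.** The documents give no rates. Assume that 10–30% of the 40 participants are women of childbearing potential and that 5–10% of participants are withdrawn at week 4.

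- Both arms: 40 × 0.10 × 0.05 = 0.2 to 40 × 0.30 × 0.10 = 1.2 women.
- Simvastatin arm, half of these: 0.1 to 0.6.
- With an assumed 1–4% chance of pregnancy over the 12 weeks: 0.1 × 0.01 = 0.001 to 0.6 × 0.04 = 0.024 exposed pregnancies in the trial.

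These counts are before removing women who decline or are unsuitable to restart.

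**The case against.** The strongest objection is that the age of the test does not set the restart apart. Women who stay on treatment also reach week 12 on a Day 0 result, mostly at 80 mg, and nothing in the documents says that restarting carries more pregnancy risk than continuing. This stands: 84 days alone is no criticism of the restart. What does set it apart is the contraception wording. For continuous users the duty plainly runs through week 12. For those withdrawn at week 4 it may not.

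A second objection is that other controls apply: effective contraception, the duty to report a pregnancy, the criteria review at telephone contacts, and the physician's and CI's judgement. These lower the risk, and a clinician may well ask for a test. None of them requires one. The information sheet, SPC, SOPs and Summary of Drug Arrangements were not available and might.

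A third is that the numbers are very small and that a test may mean an extra attendance for someone with EDSS 4.0 to 6.5. That is right, and it keeps this a minor point.

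A reader might infer that no pregnancy test at all precedes the second exposure. The documents do not support that: the Visit 1 test precedes both exposures, and only a repeat is missing.

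**Conclusion.** The point holds as a minor safety improvement. The protocol requires no repeat pregnancy test between Day 0 and a week-12 restart, and confidence in that is high. Criterion 4 can be read so that contraception ends 1 to 2 weeks before the restart.

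A reader might go further and conclude that contraception does lapse. The text does not establish this. Item 7 of 14.2 supports that reading only indirectly, and if the final stop is meant there is no lapse. Confidence that a gap would occur in practice is low.

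Probably one participant or fewer is affected, on assumed shares of women of childbearing potential and of week-4 withdrawals. The 49 to 56 days off drug assume that dosing stopped at Visit 2. Sample size, primary analysis and trial results are not affected.

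**What to change.** - In 10.2 and Appendix 1, require a negative urine dipstick and reconfirmed contraception before any week-12 restart in women of childbearing potential.
- In 8.1.1 criterion 4 and its synopsis copy, state that contraception runs until six weeks after the last dose, including any pause before a possible restart.

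The cost is an amendment, which section 27 does not allow to be implemented before approval, one dipstick of a kind the trial already uses, and possibly one extra contact or attendance.

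The SAP is dated March 2024, and the documents do not say whether dosing continues. If it has ended, check whether any such restart took place and was tested, and carry the wording into later protocols.

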11.1 Local laboratories

The following tests will be carried out at Central Laboratories (Institute of Ophthalmology).

Blood samples from these patients will be taken at baseline and at weeks 4, 16 and 20 to investigate the effect of statins on vascular leakage and free radical damage.

Biomarkers will be determined as follows: (i) For RNA/DNA oxidative damage serum levels of 8-hydroxyguanosine (8-OHG)/8-hydroxydeoxyguanosine (8-OHdG); (ii) Protein oxidative damage will be determined by assaying plasma proteins for nitrotyrosine and carbonyl content; and (iii) Detection of lipid oxidative damage by assaying for the advanced lipid peroxidation end products 4-hydroxynonenal (4-HNE)

or HNE), malondialdehyde (MDA), 8-iso-prostaglandin F2 α and thiobarbituric acid reactive substances (TBARS) (Miller et al., 2012).

All assays will be conducted using standard commercial kits (Cell Biolabs). To determine dysfunction of the blood-brain barrier (BBB) circulating levels of S100B and ubiquitin C-terminal hydrolase 1 (UCHL1) will be measured. Detection will be through the use of commercially available ELISA kits. In addition circulating cholesterol levels will be determined.

Details on handling, processing, storage and shipment of these samples are in the laboratory SOP.

The following safety blood tests will be carried out at Local Laboratories (Queens Square):

BLOOD:

Analyte	Units
SODIUM	mmol/L
POTASSIUM	mmol/L
CHLORIDE	mmol/L
UREA	mmol/L
CREATININE	umol/L
BILIRUBIN	Umol/L
ALKALINE PHOSPHATASE	IU/L
ALANINE TRANSFERASE	IU/L
CK	IU/L
TOTAL PROTEIN	g/L
ALBUMIN	g/L
GLOBULIN	g/L
TRIGLYCERIDES	mmol/L
CHOLESTEROL	mmol/L
HDL CHOLESTEROL	mmol/L
LDL CHOLESTEROL	mmol/L
ESTIMATED GFR	mL/min/1.73sqm
THYROID STIMULATING HORMONE	mIU/L
HAEMOGLOBIN	g/L
HCT	%
RED CELL COUNT	$\times 10^{12}/L$
MCV	fL
MCHC	g/L
RDW	

Analyte	Units
PLATELET COUNT	$\times 10^9/L$
MPV	fL
WHITE CELL COUNT	$\times 10^9/L$
NEUTROPHILIS	$\times 10^9/L$
LYMPHOCYTES	$\times 10^9/L$
MONOCYTES	$\times 10^9/L$
EOSINOPHILIS	$\times 10^9/L$
BASOPHILIS	$\times 10^9/L$

URINE:

Urine analysis: Pregnancy test (dipstick)

12. Clinical Procedures and Data Collection

Clinical examination will include:

Clinician observed expanded disability status score (EDSS) is a method of quantifying disability in MS and records changes in disability over time. The EDSS scale ranges from 0 (no disability) to 10 (death due to MS) in 0.5 unit increments that represent higher levels of disability. Scoring is based on an examination by a neurologist and encompasses pyramidal, cerebellar, brainstem, sensory, bowel/bladder function in addition to visual, cerebral and other functions.

MSFC inc. 9HPT, 25TFW, PASAT comprises quantitative functional measures of three key clinical aspects of MS: leg function/ambulation (25TFW), arm/hand function (9HPT), and cognitive function/working memory (PASAT). However, PASAT will not be performed in this study as the SDMT is able to measure this component.

Frontal Assessment Battery (FAB) is a concise cognitive test in neurodegenerative disease with frontal involvement.

Symbol Digit Modalities Test (SDMT) is measure of cognitive impairment. The subject is asked to match single digits to symbols using a key as a guide that pairs the numbers to the symbols. They are presented with a page headed by a key that pairs the single digits 1–9 with nine symbols and they then write or orally report their responses in a scoring form. It can be administered in oral and written form and is timed and guided by a trained examiner ie. suitably qualified member of the research team.

Patient reported multiple sclerosis impact scale version 2 (MSIS-29v2) is a self-administered questionnaire that asks to what degree the impact of MS has on a person's day-to-day life during the past two weeks.

Patient reported Multiple Sclerosis Walking Score version 2 (MSWSv2) is a self-administered questionnaire that measures walking performance.

Concomitant medication: all over-the counter or prescription medication, vitamins, and/or herbal supplements will be recorded.

MRI is a non-invasive test that produces detailed images of the brain utilising magnetic field and radio waves, without radiation.

In this study we will use ASL, a sophisticated MRI technique that measures brain cerebral blood flow, which is a process of delivering blood and nutrients to the capillary beds of the brain and the time taken by blood to reach the capillary bed.

We will also measure brain tissue loss and quantify lesion load.

All will be measured over time to determine any changes.

MRI ASL questionnaire: Brain perfusion is affected by numerous factors related to demographics, physiology, lifestyle, diet and medication use which in turn can affect the MRI analysis. This questionnaire will measure the impact of these factors on MRI.

Retinal Imaging Vascular Function Questionnaire: This is an abbreviated version of the ASL questionnaire to be provided on the day of retinal imaging. This questionnaire accounts for caffeine, tobacco, alcohol and sleep effect.

Advanced retinal imaging including OCT and AOSLO. The light sensitive layer of the back of the eye, the retina, can be affected in MS and we can image this layer in a number of non-invasive ways. OCT is a method of imaging the retina using light.

Similar to ultrasound, an OCT device shines light into the eye and detects the light which is returned, allowing us to “see” the retinal layers of the back of the eye in cross section. The same technique can be used to see the blood vessels of the retina and form a map of their locations, known as OCT Angiography. The quality of our images using these techniques is impeded by small optical changes which occur in everyone’s eyes. These small changes can be adjusted for using an “adaptive optics” imaging device, which allows us to look at the smallest blood vessels and cells in the retina in real time. We can also use standard colour photography techniques to take photos of the retinal vessels at different light wavelengths, which allows us to visualise oxygen levels within these blood vessels.

